12.1.4. Interim Monitoring Plan

The monitoring of subject safety and data quality will follow the NINDS Guidelines for Data and Safety Monitoring in Clinical Trials. An NIH-appointed Data and Safety Monitoring Board (DSMB) will meet at approximately 6-month intervals to review study progress (eg, enrollment,

site performance, subject retention, etc.) as well as blinded study data (safety and efficacy) provided by the DCC. The frequency and format of DSMB meetings, reports, and guidelines for interim analysis will be agreed upon prior to study initiation.

We propose to have one interim efficacy analysis at a time when half of the subjects have completed their Week 96 follow-up visit. For this interim analysis, we propose to use the Lan-DeMets spending function approach with O'Brien-Fleming stopping boundaries. Table 10 illustrates the proposed stopping boundaries under the assumption of 2 equally spaced analyses (one interim analysis and the planned final analysis). However, the Lan-DeMets method allows for analyses at unequal intervals and without having to pre-specify the time of any interim analyses. Hence, the proposed method has the flexibility to adapt should the DSMB request an interim analysis at an alternative time point or if the DSMB doesn't meet after exactly half of the patients complete their Week 96 assessment. We also propose to conduct a formal futility assessment at the time of the interim efficacy analysis. The futility assessment will be based on a determination of the predictive power. If this predictive power is below 20% at the time of the interim analysis, then we propose that the trial should stop for futility. In the event of early study termination because of overwhelming efficacy, all participants would be offered open-label active treatment, if feasible. The protocol and informed consent would be revised accordingly. Similar to all previous analysis, the statistical models will constrain the groups to be equal at baseline to account for vagaries in randomization that result in initial imbalance (Senn, 2013).

O'Brien-Fleming Stopping Boundaries for a Single Interim Analysis

Efficacy Analysis	Number of Subjects Completing 96 Week Follow-Up	Nominal P-Value to Conclude Efficacy
1	125	0.0104
2	250	0.0816

Commented [CCS3]: At the time we were finalizing the SAP, we realized that this was not modified to account for a significance level of 0.10 instead of 0.05.

12.2. DIRECT ACCESS TO SOURCE DATA/DOCUMENTS

By signing this protocol, the CSSPI agrees to conduct the study in an efficient and diligent manner and in conformance with this protocol; generally accepted standards of Good Clinical Practice (GCP); and all applicable federal, state, and local laws, rules and regulations relating to the conduct of the clinical study.

The CSSPI also agrees to allow monitoring, audits, NeuroNEXT CIRB review, and regulatory agency inspection of study-related documents and procedures and provide for direct access to all study-related source data and documents.

The CSSPI agrees not to seek reimbursement from subjects, their insurance providers, or from government programs for procedures included as part of the study reimbursed to the CSSPI by the NeuroNEXT CCC.

The CSSPI shall prepare and maintain complete and accurate study documentation in compliance with GCP standards and applicable federal, state, and local laws, rules, and regulations; and, for

each subject participating in the study, provide all data, and upon completion or termination of the clinical study submit any other reports to the Sponsor, or its designee, as required by this protocol or as otherwise required pursuant to any agreement with the Sponsor.

Study documentation will be promptly and fully disclosed to the Sponsor, or its designee, by the CSSPI upon request and shall also be made available at the CSSPI's site upon request for inspection, copying, review, and audit at reasonable times by representatives of the Sponsor or any regulatory agencies. The CSSPI agrees to promptly take any reasonable steps that are requested by the Sponsor, or its designee, as a result of an audit to cure deficiencies in the study documentation and worksheets/CRFs.

The CSSPI will promptly inform the Sponsor or its designee of any regulatory agency inspection conducted for this study.

Persons debarred from conducting or working on clinical studies by any court or regulatory agency will not be allowed to conduct or work on this Sponsor's studies. The CSSPI will immediately disclose in writing to the Sponsor or its designee if any person who is involved in conducting the study is debarred, or if any proceeding for debarment is pending or, to the best of the Investigator's knowledge, threatened.

In the event the Sponsor prematurely terminates a particular study site, the CSSPI will promptly notify the NeuroNEXT CIRB.

12.3. Study Monitoring

This study will be monitored at all stages of its development by the DCC at The University of Iowa, and clinical research personnel employed by the Sponsor or its representative. Monitoring will include on-site, and centralized monitoring to assure that the investigation is conducted according to protocol, to protect subject rights and safety, and to confirm data integrity and quality.

On-site monitoring will assess critical study procedures, including study data endpoints, subject safety, protocol compliance, and Regulatory compliance, and will involve the following:

- a. Audit data listings to source documentation.
- b. Ensure subject eligibility
- c. Verify reporting of adverse events.
- d. Assess investigational product accountability
- e. Assess compliance with protocol.
- f. Audit regulatory files
- g. Ensure adequate site personnel training

Investigators are required to store all source documents.

Centralized monitoring processes at the DCC occur at regular intervals, and will include:

- Data quality checks resulting in reports by:
 - monitoring of the data entry system

- use of data entry quality controls
- use of an online query system
- use of an eCRF (electronic case report form) management module
- Site performance checks resulting in reports by:
 - Production of data trend analyses to recognize patterns and trends
 - Use of an eCRF management module to monitor data quality
- Safety reporting monitoring, resulting in scheduled reports
- Regulatory document tracking, using an online system to upload and store regulatory documents
 - Results in reports listing missing documents and pending renewals

12.4. Audits and Inspections

The CSSPI and appropriate personnel may be periodically requested to attend meetings/workshops organized by the Sponsor or its designee to assure acceptable protocol execution. The study may be subject to audit by the Sponsor/designee or by regulatory authorities. If such an audit occurs, the CSSPI must agree to allow access to required subject records. By signing this protocol, the Investigator grants permission to personnel from the Sponsor, its representatives, and appropriate regulatory authorities for on-site monitoring and auditing of all appropriate study documentation, as well as on-site review of the procedures employed in CRF generation, where clinically appropriate. The CSSPI has to inform the Sponsor if he/she is approached for a regulatory audit.

12.5. Institutional Review Board (IRB)

Before initiation of the study, the CSSPI must obtain approval or favorable opinion of the research protocol, informed consent form (ICF), and any advertisement for subject recruitment from the NeuroNEXT CIRB complying with the provisions specified in the Code of Federal Regulations (CFR) 21 Part 56 and applicable government regulations. The Investigator must assure CIRB compliance with the applicable regulations.

A copy of written CIRB approval of the protocol, ICF, and advertising (if applicable) must be provided to the Sponsor or their designee prior to initiation of the study.

12.6. Study Documentation

By signing a copy of Form FDA 1572, the Investigator acknowledges that he/she has received a copy of the investigational drug brochure on MN-166 and assures the Sponsor that he/she will comply with the protocol and the provisions stated in Form FDA 1572. No changes in this protocol can be made without the Sponsor's written approval.

The Investigator will supply the NeuroNEXT CCC with the following:

1. Original, signed Form FDA 1572
2. Curricula vitae for all Investigators listed on Form FDA 1572

3. Copy of the Investigator's medical licensure/medical registration number
4. Signed protocol signature page
5. Signed IB signature page
6. Financial disclosure forms for everyone listed on the FDA 1572.

13. QUALITY CONTROL AND QUALITY ASSURANCE

By signing this protocol, the Sponsor and Clinical Study Sites Principal Investigator agree to be responsible for implementing and maintaining quality control and quality assurance systems with written standard operating procedures (SOPs) reviewed and approved by the NeuroNEXT network to ensure that studies are conducted and data are generated, documented, and reported in compliance with the protocol, accepted standards of GCP, and all applicable federal, state, and local laws, rules and regulations relating to the conduct of the clinical study.

14. ETHICS

14.1. Ethics Review

Documented approval from the NeuroNEXT CIRB will be obtained for all participating centers prior to clinical trial start, according to ICH (International Conference on Harmonisation) GCP, local laws, regulations and organization. When necessary, an extension, amendment or renewal of the CIRB approval must be obtained.

14.2. Ethical Conduct of the Study

The procedures set out in this clinical trial protocol pertaining to the conduct, evaluation, and documentation of this clinical trial, are designed to ensure that the Sponsor and Principal Investigator abide by Good Clinical Practice Guidelines (GCP in the appropriate current version). The clinical trial will also be carried out in accordance with applicable local law(s) and regulation(s). This may include an inspection by representatives from the NeuroNEXT CCC, DCC, MediciNova Inc. and/or Regulatory Authority representatives at any time. The CSSPI must agree to the inspection of clinical trial-related records by the NeuroNEXT CCC/ DCC/Regulatory Authority/ MediciNova, Inc. representatives, and must allow representatives direct access to source documents.

14.3. Written Informed Consent

An information and consent form will be provided to the subject. The process of obtaining informed consent must be in accordance with applicable regulatory requirements, and must adhere to GCP and ethical principles in the Declaration of Helsinki. Written informed consent must be obtained and documented before any clinical trial-specific procedure takes place. Participation in the clinical trial and date of informed consent given by the subject must be documented in the subject files.

15. DATA HANDLING AND RECORDKEEPING

15.1. Review of Records

The results from Screening and data collected during the study will be recorded in the subject's CRF, which will be designed and provided by the sponsor or a designee. The Investigator will review all CRFs. The CRFs will be signed by the CSSPI or a sub-Investigator who is listed on the Form FDA 1572 if the CSSPI is unavailable. In order to maintain confidentiality, the subject will be identified only by his/her subject number and initials.

15.2. Retention of Records

The CSSPI must arrange for retention of study records at the site for at least two years after the New Drug Application (NDA) is approved or Investigational New Drug (IND) is withdrawn, as required by the US Food and Drug Administration (FDA) regulations, or in accordance with local and/or national requirements, whichever is longer. The CSSPI should take measures to prevent accidental or premature destruction of these documents. Documents cannot be destroyed without written Sponsor authorization. The Sponsor will inform the CSSPI when the destruction of documents is permitted.

16. ADMINISTRATIVE AND REGULATORY DETAILS

16.1. Protocol Amendments and Study Termination

All revisions and/or amendments to this protocol must be approved in writing by the Protocol Steering Committee, NINDS, DSMB, and the CIRB. The CSSPI will not make any changes to the conduct of the study or the protocol without first obtaining written approval from the Sponsor and the CIRB, except where necessary to eliminate an apparent immediate hazard to a study subject.

16.2. Discontinuation of the Study

The NeuroNext Network, in collaboration with the company and DSMB, if appropriate, reserve the right to discontinue the study at site(s) for safety or administrative reasons at any time. For example, a site that does not recruit at an acceptable rate may be discontinued. Should the study be terminated and/or the site closed for whatever reason, all documentation and study medication pertaining to the study must be returned to the Sponsor or its representative.

16.3. Compliance with Financial Disclosure Requirements

By signing this protocol, the CSSPI agrees to provide to the Sponsor accurate financial information to allow the Sponsor to submit complete and accurate certification and disclosure statements as required by the US FDA regulations (21 CFR Part 54). The CSSPI further agrees to provide this information on a Financial Disclosure/Certification Form that is provided by MediciNova Inc. The Investigator will update this information if there are any relevant changes during the conduct of the study and for one year after completion of the study. This requirement also extends to sub-Investigators. The CSSPI also consents to the transmission of this information to MediciNova Inc. for these purposes.

18. APPENDICES

Appendix 1: Laboratory Safety Tests for Ibudilast/MN-166

Appendix 2: Suicide Behaviors Questionnaire-Revised (SBQ-R)

Appendix 3: Beck Depression Inventory-Fast Screen (BDI-FS)

Appendix 4: Modeled Informed Consent

Appendix 5: DSMB Guidelines

Appendix 1: Laboratory Safety Tests for Ibutilast (MN-166)

Blood Chemistry Tests
aspartate aminotransferase (AST)
alanine aminotransferase (ALT)
albumin
alkaline phosphatase
bicarbonate
blood urea nitrogen
calcium
chloride
creatinine
gamma-glutamyl transferase (GGT)
phosphorous
potassium
sodium
total bilirubin ^a
total protein
lactate dehydrogenase

Blood Chemistry Tests
triglyceride
Lipid Profile
fasting (non-random) serum cholesterol
fasting (non-random) serum high-density lipoprotein cholesterol
fasting (non-random) serum low-density lipoprotein cholesterol
fasting glucose
Endocrine Tests
serum beta-human chorionic gonadotropin (for females of childbearing potential)
urine beta-human chorionic gonadotropin
Hematology Tests
white blood cell count
white blood cell differential
eosinophilic leukocyte count
basophilic leukocyte count
neutrophil count
lymphocyte count
monocyte count
platelet count
hemoglobin
blood hematocrit
red blood cell count
red cell distribution width
red blood cell indices:
mean corpuscular volume
mean corpuscular hemoglobin concentration
mean corpuscular hemoglobin
Urinalysis Tests
color
appearance
total ketones
urobilinogen
bilirubin
red blood cells
leukocyte esterase
nitrite
pH
protein
specific gravity
glucose
microscopic evaluation ^b

^a Bilirubin will be fractionated (direct serum bilirubin test/indirect serum bilirubin test) if elevated 2.0 times the upper limit of the normal range.

^b Microscopic evaluation will be performed if dipstick analysis indicates the presence of any significant abnormality.

Appendix 2: Suicide Behaviors Questionnaire-Revised (SBQ-R)

Patient Name _____ Date of Visit _____

Instructions: Please check the number beside the statement or phrase that best applies to you.

1. Have you ever thought about or attempted to kill yourself? (check one only)

- 1. Never
- 2. It was just a brief passing thought
- 3a. I have had a plan at least once to kill myself but did not try to do it
- 3b. I have had a plan at least once to kill myself and really wanted to die
- 4a. I have attempted to kill myself, but did not want to die
- 4b. I have attempted to kill myself, and really hoped to die

2. How often have you thought about killing yourself in the past year? (check one only)

- 1. Never
- 2. Rarely (1 time)
- 3. Sometimes (2 times)
- 4. Often (3-4 times)
- 5. Very Often (5 or more times)

3. Have you ever told someone that you were going to commit suicide, or that you might do it?

- 1. No
- 2a. Yes, at one time, but did not really want to die
- 2b. Yes, at one time, and really wanted to die
- 3a. Yes, more than once, but did not want to do it
- 3b. Yes, more than once, and really wanted to do it

4. How likely is it that you will attempt suicide someday? (check one only)

- 0. Never
- 1. No chance at all
- 2. Rather unlikely
- 3. Unlikely
- 4. Likely
- 5. Rather likely
- 6. Very unlikely

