8.8.2.14.8. Suicide Behaviors Questionnaire-Revised (SBQ-R)

The 4-item SBQ-R is a measure of past suicidal thoughts and attempts which have proved to be significant predictors of future suicidality. The items ask if the respondent has ever thought about or attempted suicide, how frequent was suicidal thoughts in the past year, have they told someone about such thoughts, and what is the likelihood of attempting suicide in the future.

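### SBQ-R item 4 in Appendix 2 gives its top code a low-likelihood label, so a recorded 6 is ambiguous and the highest likelihood has no answer

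*Combined protocol and SAP*

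**What the plan says.** Protocol Section 8.8.2.14.8 describes the SBQ-R as a four-item measure of past suicidal thoughts and attempts, which it calls "significant predictors of future suicidality". It lists the content of the last item as "what is the likelihood of attempting suicide in the future".

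Appendix 2 prints the form. The subject is told: "Please check the number beside the statement or phrase that best applies to you". Item 4 offers seven options, coded 0 to 6. The third is "2. Rather unlikely", the sixth is "5. Rather likely", and the seventh and last is "6. Very unlikely".

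Table 1 schedules the form 12 times, at Baseline and at each visit through Week 100. Table 2 adds it at relapse evaluations, at early withdrawal, and at the semi-annual visits of subjects who have stopped study drug. The SAP does not mention the SBQ-R.

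**The concern.** The subject completes this form by matching a printed label to a number. On item 4 the label beside the highest number points the opposite way from the labels just before it. Someone who thinks an attempt very unlikely is led to the top code. Someone who thinks it very likely finds no label that fits.

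What is at stake is the routine check on suicidality during treatment. The only other questionnaire that asks directly about suicidal thoughts, the BDI-FS, is scheduled at screening only (Table 1). After screening, the SBQ-R is the only scheduled suicidality questionnaire, and item 4 is the only one of its four items that asks about the future. For subjects who stop study drug but stay in follow-up, new-onset adverse events are no longer collected (Sections 7.3.1 and 11.4), while the SBQ-R continues. An answer that cannot be read matters more there.

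**Working it through.** The plan states no figure on this point, so there is none to reproduce. The check is whether labels and codes run in one direction.

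**Item 4, label against code (Appendix 2)**

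| Codes | What the labels convey | Movement |
|---|---|---|
| 0, 1 | no likelihood | start |
| 2, 3 | unlikely (code 2: "2. Rather unlikely") | up |
| 4, 5 | likely (code 5: "5. Rather likely") | up |
| 6 | "6. Very unlikely" | down |

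Across codes 0 to 5 the labels move from none to likely. The step from 5 to 6 goes back to the unlikely side. No option carries a label stronger than code 5.

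**Items 1 to 3 on the same form.** Item 1 runs from never having thought of suicide to having attempted it and hoped to die. Item 2 runs from never to five or more times in the past year. Item 3 runs from having told no one to having told someone more than once and meant it. All three put the greater concern at the higher code. That code 6 of item 4 is meant as the highest likelihood is an inference from this pattern and from codes 0 to 5; the documents do not say it outright.

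**Is the label corrected or explained elsewhere?** Section 8.8.2.14.8 gives only the topic of the item. Neither the protocol nor the SAP describes reverse scoring, a total score, a cut-off or an action trigger.

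**Size for one subject.** Assume, for illustration, that the number checked is the item score.

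- A subject who thinks an attempt very unlikely and follows the label records 6. On the form's own order the fitting code would be about 2 or 3, so the record is 6 − 3 = 3 to 6 − 2 = 4 points too high.
- A subject who thinks an attempt very likely and follows the labels can record at most 5. If the top code was meant for that answer, the record is 6 − 5 = 1 point too low.
- A subject who goes by position rather than label, and takes the last option as the most likely, also records 6.

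The first and third subjects leave the same entry with opposite meanings. That is why a recorded 6 cannot be interpreted on its own.

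**The case against.** The strongest reply is that this is one wrong word in an appendix and that its consequences are easily overstated. Much of that stands.

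- A reader might infer that high-risk patients will be missed and low-risk patients falsely flagged. The documents do not support a statement that strong. With no scoring rule or threshold there is no defined flag, and a subject at high risk can still choose either of the two likely options. Items 1 to 3 are intact and cover plans and attempts, frequency over the past year, and communicated intent. Adverse events are also reviewed at scheduled visits while the subject is on drug.
- A reader might infer that every form is affected: 12 visits × 250 subjects = 3,000. That counts forms handed out under the full schedule, not answers altered. Only subjects who check 6, or who would have chosen a true top category, are touched, and the documents give no basis for that number. Subjects who stop drug also move to fewer visits.
- A reader might infer that all item 4 answers are unusable. A low-risk subject reading down the list meets four fitting options (codes 0 to 3) before reaching code 6, and those labels agree with their order.
- A reader might infer raised risk because the trial screens for depression. Exclusion 20 removes moderate to severe depression by the BDI-FS, which has its own item on suicidal thoughts.

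The text was also extracted from a PDF, so a misread word cannot be wholly excluded. The line is complete and shows no damage, and checking the issued form settles it.

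None of this makes the printed order coherent or supplies the missing top option.

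**Conclusion.** The point holds as a labelling error in a subject-completed safety form. Code 6 of item 4 contradicts the order of the codes below it and the direction of items 1 to 3. A recorded 6 is ambiguous, and a recorded 5 may understate the answer of a subject who found nothing stronger to check.

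The number of subjects affected cannot be derived from the documents. The effect is confined to safety monitoring: the SBQ-R is not an endpoint, not the eligibility screen and not an SAP analysis variable, so no efficacy or planned safety analysis changes. The error is clerical, but it deserves correction because it sits in the only suicidality questionnaire scheduled after screening.

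The conclusion rests on two assumptions: that Appendix 2 is the form sites use, and that the codes of item 4 are meant to rise with likelihood.

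**What to change.** Check Appendix 2 and the form actually issued to sites against the source instrument, and reconcile the label of code 6 with the code order.

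If the issued form is correct, only the appendix needs amending. If the faulty form was used, issue the corrected page, notify sites, and review recorded answers of 6, and of 5 where relevant. Answers at lower codes can stand.

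No extra visit is needed to repeat the question, because the next scheduled visit asks it again. For subjects on the semi-annual schedule that may be up to 24 weeks away, and for those past Week 100 there is no later visit, so the data review matters most for them.

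The cost is one form correction, a site notice and a short data review.
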